3.3 Safety Information

[figure not shown]
Adalimumab therapy has a well established and well described safety profile in adults based on extensive postmarketing experience and continued clinical trial-subject exposure since the first approved indication in 2002 for rheumatoid arthritis. In general, the safety profile observed in pediatric studies is consistent with that in the adult population. A detailed discussion of the pre-clinical toxicology, metabolism, pharmacology and safety experience with adalimumab can be found in the current Investigator's Brochure. AbbVie is committed to continue to collect safety information including those events that may occur in this trial in order to confirm this established safety profile and to identify any unknown potential adverse reactions, rare events and those events with a long latency.

3.4 Benefits and Risks

Extensive clinical and postmarketing experience exists with adalimumab in a wide range of disease states including the IBD indications Crohn's disease and UC. The safety profile of adalimumab in those indications is well established with more than 50,000 patient-years of adalimumab clinical trial experience. The clinical studies in adult UC have not altered this safety profile and demonstrated a positive benefit/risk balance.

Conditions which may present a risk specifically for subjects with UC are exclusion criteria in this study (e.g., evidence of colonic dysplasia or active infections).

Considering the coronavirus (COVID-19) pandemic, the benefit and risk to subjects participating in this study has been re-evaluated. Subjects receiving adalimumab may be at an increased risk for COVID-19 infection or experience serious illness if infected. Management of these adverse events will be made on a case-by-case basis with consideration of benefit/risk. However, based on the population and disease being studied and the anticipation that COVID-19 related risks are not expected to differ substantially between study subjects and the broader population of subjects receiving treatment for ulcerative colitis, no change to the benefit/risk balance for subjects in this study is expected. Current published information suggests that the baseline use of biologics is not associated with worse Covid-19 outcomes.²⁰

4.0 Study Objective

[figure not shown]
The objective of the study is to evaluate the long-term safety, tolerability, and maintenance of clinical response, of repeated administration of adalimumab in pediatric subjects with ulcerative colitis who participated in, and successfully completed, Protocol M11-290 through Week 52.

5.0 Investigational Plan

5.1 Overall Study Design and Plan: Description

The study was designed to enroll approximately 85 subjects from the main study and approximately 8 subjects from the Japan sub-study to meet scientific and regulatory objectives without enrolling an undue number of subjects in alignment with ethical considerations.

Fifty-five pediatric subjects with moderate-to-severe ulcerative colitis who participated in, and successfully completed, Protocol M11-290 through Week 52 will be enrolled at 11 sites worldwide (Section 5.3.1.1).

There also will be 4 Japanese subjects in a Japan sub-study to be enrolled at 3 Japan sites. The Japan sub-study will be conducted utilizing the same design as outlined in the main study with the exceptions that are outlined in a separate Japan specific protocol.

Subjects who meet all of the inclusion criteria and none of the exclusion criteria will be enrolled into the study and will receive open-label study drug. At the Baseline visit, the following procedures will be completed as part of Week 52 of the M11-290 protocol: concomitant medication updates, physical exam, vital signs, Chemistry/hematology, hs-CRP, urinalysis, pregnancy test, TB testing, Mayo Score, PMS, PUCAI, IMPACT III Questionnaire, WPAI UC-Caregiver, Tanner Stage, Anthropometric Evaluations, endoscopy and monitoring of adverse events as well as subject diary dispensing/reviewing. Medical History will be updated from the medical history recorded during the subject's previous study.

[figure not shown]
All subjects will receive open-label therapy as follows beginning at the Baseline Visit in Study M10-870:

Prior to Amendment 4:

- Subjects who enrolled into the study from blinded treatment in Study M11-290 were to receive open label 0.6 mg/kg (maximum of 40 mg) eow of adalimumab.
- Subjects who received open label 0.6 mg/kg (maximum of 40 mg) ew of adalimumab in Study M11-290 were to maintain the same dose in Study M10-870.

After Amendment 4, ongoing subjects will be switched to receive a fixed-dose regimen, by weight cut-off, incorporating citrate free adalimumab in PFS (20 mg, 40 mg, or 80 mg) as follows:

• Subjects with a body weight < 25 kg will receive open label 20 mg eow of adalimumab

- Subjects with a body weight \geq 25 kg < 40 kg will receive open label 40 mg eow of adalimumab
- Subjects with a body weight ≥ 40 kg will received open label 80 mg eow of adalimumab.

Ongoing subjects will continue to administer the remainder of dispensed vials as per the dose regimen prior to Amendment 4 until their first visit with Study Drug Dispensing after Amendment 4 when they will transition to the fixed dose regimen.

[figure not shown]
The duration of the study could be up to 298 weeks, which includes a 288-week open-label maintenance period and a 70-day follow-up. There is a \pm 3 day window for all study visits. An effort will be made to bring subjects back to their original scheduled visit (calculated from Baseline) if they are out of the visit window.

Efficacy and safety measurements will be performed throughout the study (see Table of Activities, Section 5.3.1). Clinical evaluation will be performed at Baseline, Weeks 4, 8, 12, 24, 36, 48, 60, 72, 84, 96, 108, 120, 144, 168, 192, 216, 240, 264 and 288/Premature Discontinuation and unscheduled Visits. Subjects may undergo an optional endoscopy during Weeks 48, 96, 192, and 288/Premature Discontinuation Visit to assess disease activity and for surveillance per the investigator's discretion.

Treatment of Subjects with a Disease Flare

Criteria for Disease Flare are as follows:

- Subjects with a Baseline Study M10-870 PMS of 0 to 2 who present with a PMS at least 3 points greater than their Baseline Study M10-870 score.
- Subjects with a Baseline Study M10-870 PMS of 3 to 4 who present with a PMS at least 2 points greater than their Baseline Study M10-870 score.
- Subjects with a Baseline Study M10-870 PMS of 5 to 6 who present with a PMS at least 1 point greater than their Baseline Study M10-870 score.
- Subjects who present with a PMS of at least 2 points greater than their PMS at the previous visit and who are not in remission per PMS.

Prior to Amendment 4:

- Subjects with a disease flare who were on 0.6 mg/kg (maximum dose of 40 mg, weight based) eow of adalimumab could receive 0.6 mg/kg (maximum of 40 mg, weight based) ew of adalimumab.
- Subjects with a disease flare who were on 0.6 mg/kg ew of adalimumab could receive 40 mg ew (maximum dose of 40 mg).

Subjects with persistently uncontrolled disease while on adalimumab 40 mg ew (max dose) were to be discontinued from the study.

After Amendment 4:

[figure not shown]
- Subjects who are on 20 mg eow of adalimumab may receive 40 mg eow of adalimumab.
- Subjects who are on 40 mg eow of adalimumab may receive 80 mg eow of adalimumab.

Subjects with persistently uncontrolled disease while on adalimumab 80 mg eow should be discontinued from the study.

The Investigator should consider dose escalation in lieu of initiating any rectal therapy such as therapeutic enemas or suppositories during the study. The AbbVie study designated physician identified in Section 6.1.7 should be contacted if there are any questions regarding rectal therapy.

Dose De-Escalation and Re-Escalation

Subjects who have been in remission (PMS \leq 2 with no individual subscore > 1) for at least 8 weeks and for at least 2 consecutive visits may have their dosage decreased from ew to eow prior to Amendment 4 or to the next lower dose after Amendment 4. The investigator should receive prior approval from the medical monitor before taking any action with regard to dose de-escalation.

Subjects who demonstrate disease flare after dose de-escalation have the opportunity to re-escalate their dose back to adalimumab ew dosing prior to Amendment 4 or to the next higher dose after Amendment 4. The investigator should receive prior approval from the medical monitor before taking any action with regard to dose re-escalation. One de-escalation within a period of 48 weeks and one re-escalation within a period of 48 weeks are permissible.

No study drug will be administered or injected at the final visit.

Subjects may discontinue adalimumab treatment at any time during study participation. Subjects that end study participation early will have a Termination Visit. All subjects will have a follow-up phone call approximately 70 days after the last administration of study drug to obtain information on any new or ongoing AEs.

[figure not shown]
An Example of 70-Day Follow-Up Call – Form is described in Appendix G.

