After Amendment 4, ongoing subjects will be switched to receive citrate free adalimumab in PFS of 20 mg, 40 mg, or 80 mg as follows:

- Subjects with a body weight < 25 kg will receive open label 20 mg eow of adalimumab
- Subjects with a body weight ≥ 25 kg < 40 kg will receive open label 40 mg eow of adalimumab
- Subjects with a body weight \geq 40 kg will receive open label 80 mg eow of adalimumab.

Ongoing subjects will continue to administer the remainder of dispensed vials as per the dose regimen prior to Amendment 4 until their first visit with Study Drug Dispensing after Amendment 4 when they will transition to the fixed dose regimen. Subjects who demonstrate a disease flare may have their dosage adjusted.

Prior to Amendment 4:

- Subjects who were on 0.6 mg/kg (maximum dose of 40 mg) eow of adalimumab could receive 0.6 mg/kg (maximum of 40 mg) ew of adalimumab
- Subjects who were on 0.6 mg/kg ew of adalimumab could receive 40 mg ew of adalimumab (max dose)

After Amendment 4:

- Subjects who are on 20 mg eow of adalimumab may receive 40 mg eow of adalimumab
- Subjects who are on 40 mg eow of adalimumab may receive 80 mg eow of adalimumab

Criteria for Dose Escalation (Increase) of Subjects with Disease Flare:

[figure not shown]
- Subjects with a Baseline Study M10-870 PMS of 0 to 2 who present with a PMS at least 3 points greater than their Baseline Study M10-870 score.
- Subjects with a Baseline Study M10-870 PMS of 3 to 4 who present with a PMS at least 2 points greater than their Baseline Study M10-870 score.
- Subjects with a Baseline Study M10-870 PMS of 5 to 6 who present with a PMS at least 1 point greater than their Baseline Study M10-870 score.
- Subjects who present with a PMS of at least 2 points greater than their PMS at the previous visit and who are not in remission per PMS.

Prior to Amendment 4, subjects with persistently uncontrolled disease while on adalimumab 40 mg ew (max dose) were to be discontinued from the study.

After Amendment 4, subjects with persistently uncontrolled disease while on adalimumab 80 mg eow should be discontinued from the study.

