5.2 Selection of Study Population

5.2.1 Inclusion Criteria

A subject will be eligible for study participation if he/she meets all of the following:

- 1. Subject must have successfully enrolled in and completed Protocol M11-290 through Week 52.
- 2. Subject of legal age, and/or parent or legal guardian, as required, has voluntarily signed and dated an Institutional Review Board (IRB)/Independent Ethics Committee (IEC) approved informed consent form, after the nature of the study has been explained and the subject of legal age, and/or Subject's parent, or legal guardian, as required, has had the opportunity to ask questions. The informed consent must be signed before any study-specific procedures are performed. Subjects will be included in all discussions, and if required, their signature on an assent form will be obtained.

[figure not shown]
- 3. Parent or legal guardian of subject who is not of legal age, as required, must be willing to actively supervise storage and administration of study drug and to ensure that the time of each dose is accurately recorded in the subject's electronic diary.
 - If a subject is of a legal age, subjects must be able and willing to self-administer SC injections or have a qualified person available to administer SC injections and to ensure that the time of each dose is accurately recorded in the subject's electronic diary.
- 4. If female, subject who is either not of childbearing potential, defined as pre-menstrual, or is of childbearing potential and is practicing an approved method of birth control throughout the study and for 150 days after last dose of the study drug.

Examples of approved methods of birth control include the following (see local informed consent for more detail):

- Total abstinence from sexual intercourse;
- Condoms, sponge, foam, jellies, diaphragm or intrauterine device (IUD);
- Hormonal contraceptives for 90 days prior to study drug administration;
- A vasectomized partner.
- 5. Subject is judged to be in good medical condition, as determined by the Principal Investigator based upon results of clinical and laboratory evaluations done throughout the preceding ulcerative colitis Study M11-290.

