The Mayo Score (consisting of the Partial Mayo Score plus the endoscopic subscore) will be calculated at weeks where endoscopy is performed (i.e., Week 48, 96, 192 and 288). The Partial Mayo Score and the Mayo Score (consisting of the Partial Mayo Score plus the endoscopic subscore) assessed at the Week 52 visit of Study M11-290 will be used for the Baseline assessment (prior to receiving study drug). The Mayo Score and the Script for collection of Mayo Score are described in Appendix D.

[figure not shown]
The average stool frequency subscore, rectal bleeding subscore, Partial Mayo score and Mayo score for each study visit will be recorded in the eCRF in decimal numbers.

For the purpose of disease flare assessment, Baseline PMS will be rounded up or down to the nearest full number. For example, if a patient had a PMS of 5.4 at Baseline and came in for a disease flare assessment, then the Baseline PMS would be rounded down to 5.0 for this purpose. If a patient had a PMS of 5.5 at Baseline and came in for a disease flare assessment, then the Baseline PMS would be rounded up to 6.0.

Whenever possible, the same physician (investigator or subinvestigator) should determine all Mayo Scores and Partial Mayo Scores for an individual subject through the duration of the study.

IMPACT III Questionnaire²²

Subjects 9 years of age or older at Baseline will complete an IMPACT III questionnaire at Baseline, Weeks 24, 48, 72, 96, 120, 144, 168, 192, 216, 240, 264, and 288/Premature Discontinuation Visit.

The IMPACT III questionnaire assessed at the Week 52 visit of Study M11-290 will be used for the Baseline assessment (prior to receiving study drug).

WPAI Questionnaire

Work Productivity and Activity Impairment Questionnaire (WPAI) will be completed at Baseline, Weeks 24, 48, 72, 96, 120, 144, 168, 192, 216, 240, 264, and 288/Premature Discontinuation Visit (Appendix E). The WPAI questionnaire assessed at the Week 52 visit of Study M11-290 will be used for the Baseline assessment (prior to receiving study drug).

[figure not shown]
The subject's parent or legal guardian will complete the WPAI. The questionnaire will not be completed if the subject's parents or legal guardian do/does not take care of the subject anymore.

States of Emergency or Pandemic-Related Acceptable Protocol Modifications

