5.5.1 Treatments Administered

Prior to Amendment 4, all subjects received open-label therapy as follows beginning at the Baseline Visit in Study M10-870:

- Subjects who enrolled into the study from blinded treatment in Study M11-290 were to receive open label 0.6 mg/kg (maximum of 40 mg) eow of adalimumab.
- Subjects who received open label adalimumab in Study M11-290 were to maintain the same dose in Study M10-870.

After Amendment 4, ongoing subjects will be switched to receive a fixed dose regimen, by weight cutoff, incorporating open-label citrate free adalimumab in PFS (20 mg, 40 mg, or 80 mg) as follows:

• Subjects with a body weight < 25 kg will receive open label 20 mg eow of adalimumab

- Subjects with a body weight \geq 25 kg < 40 kg will receive open label 40 mg eow of adalimumab
- Subjects with a body weight ≥ 40 kg will receive open label 80 mg eow of adalimumab

Treatment of Subjects with Disease Flare

Prior to Amendment 4:

- Subjects who were on 0.6 mg/kg (maximum dose of 40 mg, weight based) eow of adalimumab could receive 0.6 mg/kg (maximum of 40 mg, weight based) ew.
- Subjects who were on 0.6 mg/kg ew of adalimumab could receive 40 mg ew (maximum dose) of adalimumab.

[figure not shown]
Subjects with persistently uncontrolled disease while on adalimumab 40 mg ew (max dose) were to be discontinued from the study.

After Amendment 4:

- Subjects who are on 20 mg eow of adalimumab may receive 40 mg eow of adalimumab.
- Subjects who are on 40 mg eow of adalimumab may receive 80 mg eow of adalimumab.

Subjects with persistently uncontrolled disease while on adalimumab 80 mg eow should be discontinued from the study.

Consideration should be given to have the subject return to the study site for unscheduled visit in order to collect the required PMS to satisfy the definition of disease flare.

Criteria for Disease Flare are as follows:

- Subjects with a Baseline Study M10-870 PMS of 0 to 2 who present with a PMS at least 3 points greater than their Baseline Study M10-870 score.
- Subjects with a Baseline Study M10-870 PMS of 3 to 4 who present with a PMS at least 2 points greater than their Baseline Study M10-870 score.
- Subjects with a Baseline Study M10-870 PMS of 5 to 6 who present with a PMS at least 1 point greater than their Baseline Study M10-870 score.
- Subjects who present with a PMS at the current visit of at least 2 points greater than their PMS at the previous visit and who are not in remission per PMS.

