Partial Mayo Score	Composite score of UC disease activity based on the subscores of stool frequency, rectal bleeding, and physician's global assessment and DOES NOT include the endoscopic subscore. This score ranges from 0 – 9 points with higher scores representing more severe disease.	
9 point Mayo Score (without PGA)	Composite score of UC disease activity based on the subscores of stool frequency $(0-3)$, rectal bleeding $(0-3)$, and endoscopic subscore $(0-3)$. This score ranges from $0-9$ points with higher scores representing more severe disease.	
6 point Mayo Score (without PGA and endoscopy subscore)	Composite score of UC disease activity based on the subscores of stool frequency $(0-3)$ and rectal bleeding $(0-3)$. This score ranges from $0-6$ points with higher scores representing more severe disease.	

[figure not shown]

Table 2. Definition of Endpoints Based on Mayo Score and Component Scores

Term	Definition
Clinical remission per Partial Mayo Score	PMS ≤ 2 and no individual subscore ≥ 1
Clinical response per Partial Mayo Score	Decrease in PMS \geq 2 points and \geq 30% from Study M11-290-Baseline
Clinical remission per Mayo Score	Mayo score ≤ 2 and no individual subscore > 1
Clinical response per Mayo Score	Decrease in Mayo Score \geq 3 points and \geq 30% from Study M11-290-Baseline
Mucosal healing	Endoscopy subscore of 0 or 1
Clinical remission per 9 point Mayo Score (without PGA)	Defined as the 9 point Mayo Score (without PGA) \leq 2 and no individual subscore $>$ 1
Clinical remission per 6 point Mayo Score (without PGA and endoscopy subscore)	Defined as the 6 point Mayo Score (without PGA and endoscopy subscore) ≤ 1

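### The Baseline-based flare criteria stop at PMS 6 on a 0 to 9 scale, so a rise from 6 to 7 permits dose escalation while a rise from 7 to 8 may not

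*Protocol*

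**What the plan says.** The synopsis and Sections 5.1 and 5.5.1 of the protocol give the same four criteria. In the synopsis they are headed "Criteria for Dose Escalation (Increase) of Subjects with Disease Flare".

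- Three criteria compare the current PMS with the M10-870 Baseline. Baseline 0 to 2 needs a rise of at least 3 points, Baseline 3 to 4 a rise of at least 2, and the last band is "Subjects with a Baseline Study M10-870 PMS of 5 to 6 who present with a PMS at least 1 point greater than their Baseline" score. Section 5.5.1 has the same top band: "Subjects with a Baseline Study M10-870 PMS of 5 to 6".
- The fourth applies at any Baseline: "Subjects who present with a PMS of at least 2 points greater than their PMS at the previous visit", provided the child is not in remission per PMS.

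Three other provisions decide who falls into which band:

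- **Rounding.** Under Mayo Score in Section 5.3.1.1, "Partial Mayo score and Mayo score for each study visit will be recorded in the eCRF in decimal numbers". For flare assessment, however, "Baseline PMS will be rounded up or down to the nearest full number"; the worked example there takes 5.4 to 5 and 5.5 to 6.
- **Scale.** SAP Section 6.0, Table 1, defines PMS as the composite that "DOES NOT include the endoscopic subscore. This score ranges from 0" to 9 points.
- **Entry.** The first inclusion criterion is "Subject must have successfully enrolled in and completed Protocol M11-290 through Week 52". Nothing in Sections 5.2.1 or 5.2.2 caps PMS or requires response or remission at Week 52. The nearest conditions are the investigator's judgement of good medical condition and suitability, and the exclusion of fulminant colitis and toxic megacolon.

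**The concern.** The bands follow a clear idea: the more active the disease at Baseline, the smaller the worsening needed to call a flare (3, then 2, then 1 point). Above 6 the idea is dropped without explanation. The child with the most active disease loses the Baseline-based route and must show a rise of 2 points between consecutive visits, more than the 1 point asked of a child in the 5 to 6 band.

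The criteria control treatment. Section 5.5.1 advises an unscheduled visit to collect the PMS needed to meet the flare definition, so sites are expected to meet it before escalating. Section 7.0 bars intentional deviations and makes an incorrect dose reportable. Section 5.1 asks investigators to consider escalation in place of rectal therapy, yet this child may not qualify for escalation. The explicit instruction to discontinue for persistently uncontrolled disease applies only at the top dose (40 mg every week before Amendment 4, 80 mg every other week after it). A worsening child below the top dose may thus meet neither the escalation rule nor that discontinuation rule.

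**Working it through.** **Inputs.** PMS is the sum of three subscores (stool frequency, rectal bleeding, physician's global assessment), each 0 to 3 (protocol Appendix D; SAP Section 6.0). The maximum is 3 × 3 = 9, which matches the SAP. The four criteria and the rounding rule are as set out above.

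**Thresholds by rounded Baseline b.** The band threshold is b + 3 for b = 0 to 2, b + 2 for b = 3 to 4, and b + 1 for b = 5 to 6. The last column adds the fourth criterion for the case where the previous visit is Baseline, in whole-number scores and treating any PMS of 2 or less as remission. That simplification affects only the low end.

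| Rounded Baseline | Rise asked by band | Lowest PMS meeting band | Lowest PMS meeting any criterion |
|---|---|---|---|
| 0 | 3 | 3 | 3 |
| 1 | 3 | 4 | 3 |
| 2 | 3 | 5 | 4 |
| 3 | 2 | 5 | 5 |
| 4 | 2 | 6 | 6 |
| 5 | 1 | 6 | 6 |
| 6 | 1 | 7 | 7 |
| 7 | no band | none | 9 |
| 8 | no band | none | none |
| 9 | no band | none | none |

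**Reach of the fourth criterion.** It needs current ≥ previous + 2, and current cannot exceed 9, so the previous score must be 7 or less. A child with Baseline 7 who presents at 8 qualifies only if the previous visit was 6 or lower. A child with Baseline 8 who presents at 9 qualifies only if the previous visit was 7 or lower. A stepwise course of 7, 8, 9 never qualifies.

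**Effect of rounding, at Week 4 with Baseline as the previous visit.** Five-day averages move in steps of 1/5 = 0.2 and the global assessment is a whole number, so 6.4 (2.2 + 2.2 + 2) and 6.6 (2.2 + 2.4 + 2) are both attainable.

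- Baseline 6.4 rounds to 6, and the band threshold is 6 + 1 = 7.0.
- Baseline 6.6 rounds to 7 and has no band. The fourth criterion needs 6.6 + 2 = 8.6, or 7 + 2 = 9.0 if the rounded value also serves as the previous score, which the protocol does not say.
- A Baseline difference of 0.2 therefore moves the threshold by 8.6 − 7.0 = 1.6 to 9.0 − 7.0 = 2.0 points.

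**A course that never qualifies.** For 6.6, 8.0, 9.0 the steps are 1.4 and 1.0, both below 2. The total rise is 2.4 points, ending at the scale maximum.

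**The case against.** The strongest reply concerns reach, since the text and arithmetic are not in dispute.

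- **Few children, perhaps none.** Entry requires 52 completed weeks of M11-290 and an investigator's judgement of good condition, so a Baseline of 7 to 9 would be unusual. That is fair, but neither condition is a PMS limit. How M11-290 handled uncontrolled disease is not in the documents, so the frequency cannot be settled either way.
- **It is late.** Amendment 5 (synopsis dated 04 August 2021) writes its dosing changes for ongoing subjects, and Baseline scores are very probably all recorded. After Amendment 4, children of 40 kg or more go to 80 mg every other week, where no higher dose exists, so the gap matters only for those on 20 or 40 mg. A child stepped down after remission has a low PMS again and can reach the fourth criterion, though a slow rise could still miss it. All this narrows the benefit of a change; it does not make the rule right.
- **The fourth criterion often helps.** A child with Baseline 7 who improves to 4 and then reaches 6 qualifies while still below Baseline. The 1.6 to 2.0 point gap applies only when Baseline is the previous visit. Both points stand. The failure is confined to worsening in steps of less than 2 points without enough improvement first.
- **No endpoint is affected.** No efficacy endpoint in SAP Section 10.2 uses the flare definition, and nothing is tested. Only the descriptive dose-escalation counts in SAP Section 8.0 depend on it. This is a treatment-rule problem more than an analysis problem.
- **Other care remains.** Concomitant UC drugs can be changed (Section 5.2.3.2) and the investigator can withdraw a child (Section 5.4.1). The child is not left without care; the fault is in the escalation rule.

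**Conclusion.** The concern holds. All three statements of the criteria leave Baseline 7, 8 and 9 without a band, and the fourth criterion fills the gap only for a rise of at least 2 points between consecutive visits. Followed exactly, the rule lets a child going from 6 to 7 escalate and refuses one going 7, 8, 9. This reverses the logic of the bands, and no reason is given.

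The conclusion assumes that the criteria are applied as written and that rounding follows Section 5.3.1.1. The consequence is limited to children with a Baseline PMS of 6.5 or more who have a higher dose available: those on 20 or 40 mg every other week now, and those not yet on 40 mg every week before Amendment 4. Their number is unknown and may be zero. The rule should still be corrected, because it controls dosing in children and the correction is small.

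**What to change.** 1. Look first at the recorded Baseline PMS values. SAP Sections 6.0 and 7.1 already summarise Baseline PMS with its maximum, which will show whether any child is affected. No SAP change is needed.
2. In the synopsis and Sections 5.1 and 5.5.1, change the top band from *5 to 6* to *5 or more*, keeping the rise of at least 1 point. Rises from 7 to 8 and from 8 to 9 then qualify, and the child with Baseline 6.6 qualifies at 8.0.
3. Add a rule for a rounded Baseline of 9 (8.5 or more), where the band would need 9 + 1 = 10. One option is escalation for persistent activity with the medical monitor's approval. Its clinical content, and confirmation that 1 point is the right rise from 7 or 8, belong to the sponsor's physicians.

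The cost is wording in three places, with no new visits, data or analyses. As with any amendment, ethics committee approval is needed before implementation (Section 9.1). The separate Japan-specific protocol should be checked for the same bands.
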